Anesthesia for hip fracture surgery can be achieved by either general anesthesia (GA) or spinal anesthesia (SA). The potential advantages of SA include opioid-sparing effects, lessened impacts on the respiratory and gastrointestinal systems, and reduction in rates of adverse outcomes such as pneumonia, mechanical ventilation, intensive care unit (ICU) admission, venous thromboembolism (VTE), myocardial infarction (MI), stroke, transfusion, readmission, and prolonged postoperative length of stay (15, 16). However, a recent randomized control trial found no difference between SA and GA for older adults undergoing hip fracture surgery for the primary outcome of survival and recovery of ambulation at 60 days (17).

While emerging evidence shows COVID-19 infection increases mortality after hip surgery, there is a lack of research examining whether the choice of anesthetic technique modifies the postoperative mortality and morbidity of hip fracture patients with COVID-19 infection. This is particularly important due to the high mortality (35% in COVID-positive patients, vs. 2% in patients without COVID) (12), with the potential for SA to modify this risk by circumventing the need for airway interventions. SA may also offer superiority over general anesthesia for limiting aerosol generation and exposure of operating room staff (18) during the pandemic. While SA may reduce the risk of pulmonary morbidity by reducing the need for airway interventions, its motor block on accessory muscles and the need for sedation may adversely impact ventilation.

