In this study, our goal is to evaluate the adjusted association between anesthesia technique and mortality and morbidity after hip fracture surgery for patients who tested positive for COVID-19. Our primary objective is to determine for patients undergoing hip surgery with COVID-19 infection, whether SA, as compared to GA, is associated with a lower rate of mortality 30 days postoperatively. Our secondary objective is to determine whether SA, as compared to GA, is associated with a lower rate of morbidity 30 days postoperatively. To provide context for interpretation, we will describe the epidemiology of the following rates during versus before the 2020 COVID-19 pandemic (January to December 2021, compared to 2017 to 2019): 1) SA versus GA utilization for hip fracture surgery, and 2) mortality and morbidity for hip surgery patients without COVID-19 infection. Finally, we will quantify the mortality and morbidity for patients with versus without COVID-19 infection undergoing hip fracture surgery, stratified by SA and GA.

Methods

Study Design

Approval will be gained from the University of British Columbia Providence Health Care Research Ethics Board. The requirement for written informed consent will be waived for use of deidentified data. Patient information will be obtained for the retrospective cohort analysis using the NSQIP® (general dataset linked with the Hip Fracture Procedure Targeted Dataset), a prospectively-collected multicentre dataset with more than 150 clinical variables within 30 days after surgery (19). The study will be pre-registered prior to data analysis (Clinicaltrials.gov) and reported according to The Strengthening the Reporting of Observational Studies in Epidemiology (STROBE) guidelines.

Setting

The setting of this study will be patient data obtained from the multicentre generated NSQIP Hip Fracture Procedure Targeted Dataset. The period of patient data obtained will include from January 2017 through December 2021. We will omit the data from January 2020 to December 2020 given there was no reporting of COVID status during this period. Data will only be obtained from patients undergoing hip surgery with mortality and morbidity gathered for 30 days postoperatively.

Participants

Inclusion

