As patients with postoperative COVID-positive status are difficult to interpret due to variable incubation period and the possibility of COVID-19 contraction while in hospital post-operatively, we will perform sensitivity analysis using alternative definitions for the COVID-positive cohort, including 1) rows 2, 4, and 6 (i.e. laboratory confirmed preoperatively or post-operatively), 2) rows 4 and 6 (i.e. laboratory confirmed or symptomatic preoperatively), and 3) rows 2, 3, 4, 5, and 6 (i.e. suspected and laboratory confirmed anytime preoperatively or post-operatively).

Table 1

Row #	NSQIP classification	
	Preoperative COVID (within 14 days before surgery)	Postoperative COVID
1	No	No
2	No	Yes – lab confirmed
3	No	Yes – suspected
4	Yes – lab confirmed	No
5	Yes – suspected*	No
6	Yes – suspected	Yes – lab confirmed

*Suspected denotes COVID-19 infection suspected by patient preoperative pneumonia or dyspnea

Outcomes

All outcomes (please see Appendix 1 for detailed definitions) will be measured within 30 days postoperatively, with the exception of length of stay (LOS) which was the total number of days from the day of operation to the day of discharge from hospital (19).

Primary outcomes

The primary outcome is all-cause 30-day mortality following hip fracture surgery.

Secondary outcomes

Secondary outcomes are MI, stroke or cerebrovascular accident (CVA), postoperative delirium, pneumonia, acute renal failure, transfusion, being on ventilator postoperatively (>48 hours), being still in hospital >30 days, length of stay (LOS), discharge destination as home versus not home, hospital readmission, and unplanned reoperation. There will be three composite outcomes: 1) venous thromboembolism (VTE), defined as pulmonary embolism or deep venous thrombosis, 2) sepsis, defined as sepsis or septic shock, and 3) any complication listed above or death. The definitions of secondary outcomes collected from NSQIP variables are included in Appendix 1 (Data Extraction Form).

Exposure

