 1. To assess the association amongst anesthesia type and mortality in COVID-positive patients, a multivariable logistic regression will be performed using a priori exposure (SA vs. GA) and confounder variables (above) for the primary outcome of mortality. The same independent variables will be used in the multivariable logistic regressions for secondary outcomes (linear regression with log transformation for the outcome of length of stay).
4. Sensitivity and exploratory analysis include
 1. We will define the COVID-positive cohort using the additional definitions discussed above per Table 1.
 2. Cohort characteristics of the GA + SA group will be presented, and compared to the SA and GA groups. If this group consists of >1% of the respective cohort, the multivariable logistic regression for mortality will be repeated with GA+SA included as part of the GA group for the multivariable logistic regression.
 3. Repeat the primary modeling with the cohort after excluding patients with age “90” (all patients aged 90 and above are coded as 90+ in NSQIP, thus potential residual confounding)
 4. If there is sufficient sample size, subgroup analysis by sex (male only, female only) and age (<65, >=65 year old) may be performed.
 5. The degree of unmeasured confounding will be assessed using E-value and the Durbin-Wu-Hausman test.
 6. Adjustment for multiple testing for secondary outcomes, including Bonferroni, False Discovery Rate, and Holm's method
5. Sample size calculation
 1. There are approximately 10,000 patients in the NSQIP Hip fracture dataset per year. The prevalence of COVID-19 in the hip fracture patient population was 10% (thus an estimated sample size of approximately 1000 patients) (<https://www.ncbi.nlm.nih.gov/pmc/articles/PMC7495188>), with a mortality

of 36% in this population. The pre-pandemic SA:GA utilization ratio was approximately 1:4 (20). With 80% power and 0.05 alpha, the sample size required to detect a 10% absolute decrease in mortality rate with the SA exposure (from 36% to 26%) is 1064, and 525 for 14% absolute decrease in mortality rate, as calculated by the Sample Size Calculator (<https://clinicalcalc.com/stats/samplesize.aspx>).

2. For population cohort studies where logistic regression is used, the sample size recommended is at least 500 patients, or $100 + 50i$ (i =number of independent variables in the final model) (26). With an estimated sample size of 1000 patients, 18 independent variables can be included.

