3. Sample size calculated based on R-squared (variance explained by the multi-variable logistic regression) and mortality difference between SA vs. GA (Table 2). Assumptions are: alpha = 0.05, baseline mortality rate 36%, ratio of SA:GA of 1:4. For example, with approximately 500-1000 patients from NSQIP, the study would likely be able to detect a 12 to 14% mortality difference depending on the R-squared.

Table 2. Sample size calculation for logistic regression using G*Power software.

Amount of R ² accounted for by covariates	Detectable difference in mortality			
	8%	10%	12%	14%
0.1	1820	1139	771	552
0.2	2048	1281	868	621
0.3	2340	1464	992	709
0.4	2730	1708	1157	827

1.

Data will be analyzed using R. Significance level will be set at P <0.05.

List of variables in cohort characteristics include but are not limited to (Please see Appendix 1 for details)

Patient characteristics: Age, sex, race, body mass index (BMI) (calculated from height and weight in NSQIP), American Society of Anesthesiologists (ASA) Physical Status (PS), smoker within one year preoperatively, severe obstructive chronic pulmonary disease (COPD), dyspnea, coagulopathy, congestive heart failure (CHF), hypertension on medications, preoperative renal failure (acute renal failure, dialysis, and/or GFR < 60 mL/min/1.73 m² based on preoperative creatinine) (25), diabetes, ascites, preoperative functional status, preoperative dementia/delirium, systemic sepsis, preoperative use of mobility aid, and preoperative pressure sore.

Surgical factors: Total operating time, year of surgery, hip fracture type, pathological fracture, and days from hospital admission to operation.

Systems factors: Medical co-management, and participation in a standardized hip fracture care program.

Postoperative variables:

- Mortality
- Myocardial infarction
- Stroke/CVA
- Postoperative delirium
- VTE (composite: pulmonary embolism, DVT)
- Pneumonia
- On ventilator >48h postoperatively
- Acute renal failure
- Sepsis or septic shock (composite of systemic sepsis and septic shock)
- Transfusion (packed red blood cell (PRBC) within the first 72 hours of surgery start time)
- Readmission: also present % unplanned
- Unplanned reoperation
- Still in Hospital > 30 Days
- Non-home discharge
- Weight bearing as tolerated (WBAT) on postoperative day (POD) #1
- Wound issues (composite: superficial and deep infection, wound disruption)
- New postoperative pressure sore
- Urinary tract infection

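### Readmission is modelled over 30 days from surgery and without the unplanned qualifier, so its odds ratio partly reflects survival and length of stay rather than post-discharge morbidity

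*Combined protocol and SAP*

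**What the plan says.** The list under Secondary outcomes ends with "discharge destination as home versus not home, hospital readmission, and unplanned reoperation". The qualifier attaches to reoperation only. The list of postoperative variables at the end of the Statistical Analysis section has "Readmission: also present % unplanned", so the unplanned share is available but appears only as a descriptive addition.

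The opening of the Outcomes section says that all outcomes "will be measured within 30 days postoperatively, with the exception of length of stay (LOS". Readmission is not exempted, so its clock starts at surgery. This follows the data source, which Study Design describes as having "more than 150 clinical variables within 30 days after surgery".

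Statistical Analysis, item 3, gives the model: "The same independent variables will be used in the multivariable logistic regressions for secondary outcomes". The plan mentions no days at risk, no restriction to discharged patients and no competing event for readmission. Remaining in hospital beyond 30 days is a separate secondary outcome.

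The detailed definitions are placed elsewhere: "The definitions of secondary outcomes collected from NSQIP variables are included in Appendix 1 (Data Extraction Form". That appendix is not in the text available for this review.

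**The concern.** There are two linked problems.

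The first is time at risk. A patient discharged on day 6 has 24 days in which a readmission can be recorded, and one discharged on day 24 has 6. A patient who dies before discharge or is still an inpatient at day 30 has none. The binary outcome codes the last two as not readmitted, as if they had done well. Mortality is the primary outcome and LOS a secondary one, so the study itself asks whether time at risk depends on anesthetic technique. If it does, the readmission odds ratio mixes post-discharge morbidity with the opportunity to be readmitted.

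The second is content. The secondary objective is morbidity. Counting planned returns adds events that are not complications and is inconsistent with how reoperation is defined. Readmission also stands in the list that precedes the composite of "any complication listed above or death", so it may feed that composite too.

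At stake is the interpretation of one secondary outcome. The primary outcome is unaffected.

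**Working it through.** **Inputs from the plan.** Mortality 36% (GA) and 26% (SA), SA:GA of about 1:4, and about 1000 COVID-positive patients (Sample size calculation, item 1), hence about 200 SA and 800 GA. The plan states no figure for readmission or LOS.

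**The plan's own figure.** The pooled two-proportion formula (two-sided 0.05, 80% power, 1:4) gives 213 + 852 = 1065 for 36% versus 26%, against 1064 stated. For 36% versus 22% it gives 106 + 424 = 530, against 525. Both reproduce closely. They concern mortality and do not bear on readmission.

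**Assumptions.** The same readmission hazard after discharge in both groups, so the true post-discharge ratio is 1.00. One LOS value per group. A risk of 8% over 30 days out of hospital, so the daily hazard is h = −ln(0.92)/30 = 0.00278.

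**Step 1: LOS alone, no deaths.** Observed risk = 1 − exp(−h × (30 − LOS)).

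| LOS, SA vs GA (days) | Days at risk | Observed risk | Odds ratio | Odds ratio, front-loaded hazard |
|---|---|---|---|---|
| 5 vs 6 | 25 vs 24 | 6.71% vs 6.45% | 1.04 | 1.03 |
| 6 vs 8 | 24 vs 22 | 6.45% vs 5.93% | 1.09 | 1.06 |
| 7 vs 10 | 23 vs 20 | 6.19% vs 5.41% | 1.16 | 1.09 |
| 8 vs 13 | 22 vs 17 | 5.93% vs 4.62% | 1.30 | 1.17 |

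The last column uses a Weibull hazard with shape 0.6. Taking 5% or 12% instead of 8% changes the constant-hazard odds ratios by less than 0.01. If SA stays were the longer ones, the ratios invert: 8 versus 6 days gives 1/1.094 = 0.91.

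**Step 2: chance of a misleading result.** With 200 SA and 800 GA patients, and assumed risks of 5% to 12%, the probability of p < 0.05 against SA from this effect alone is about 3% to 8% for gaps of 1 to 3 days. It is 10% to 17% for a 5-day gap. Chance alone gives 2.5%.

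**Step 3: deaths alone, equal LOS.** Patients who die before discharge contribute no readmissions, so the risk ratio is the ratio of the shares discharged alive, whatever the readmission risk.
- All deaths before discharge: 0.74/0.64 = 1.16.
- Half of deaths before discharge: 0.87/0.82 = 1.06 (ignoring follow-up lost to later deaths).

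**Step 4: both together.** For LOS 6 versus 8, the risk ratio from step 1 is 0.0645/0.0593 = 1.088. Multiplied by step 3, this is 1.088 × 1.156 = 1.26 if all deaths precede discharge, and 1.088 × 1.061 = 1.15 if half do.

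**Step 5: would an offset for days at risk correct this?** Only under a constant hazard. With the front-loaded hazard above, the rate ratio per day at risk is (days SA / days GA)^(0.6 − 1). For LOS 6 versus 8 this is (24/22)^(−0.4) = 0.97, and for 8 versus 13 it is (22/17)^(−0.4) = 0.90. The offset over-corrects and would show a spurious benefit of SA.

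**The case against.** The strongest defence is that the risk of readmission by postoperative day 30 is a coherent total effect of technique. It shares its clock with the other 30-day outcomes and is dictated by a dataset that ends at that point. More days at home can produce more real readmissions. This stands, and it is why the surgery-anchored model should be kept. It does not make the estimate a measure of post-discharge morbidity.

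A reader might go further and infer that the analysis will make SA look harmful because SA patients go home earlier. The documents do not support that. The background lists among the potential advantages of SA a reduction in "transfusion, readmission, and prolonged postoperative length of stay (15, 16", with no figures. The same sentence posits less readmission, which could outweigh the artefact. If stay and survival are equal there is no artefact, and if SA stays are longer the LOS part reverses.

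A reader might also take it as settled that planned readmissions are in the modelled outcome. That is the plain reading of the two lists, but Appendix 1 could define it otherwise. Nothing in the documents shows how common planned readmissions are.

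Finally, replacing the model with a rate among discharged patients would condition on survival and discharge, both of which follow exposure, and a log-days offset can over-correct (step 5). That objection stands against replacement, but not against a supportive analysis. Reporting LOS and prolonged hospital stay alongside helps a reader see the issue but does not correct the estimate.

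**Conclusion.** The point holds in a limited form. The surgery-based window and the plain logistic model are explicit. It follows that in-hospital deaths and day-30 inpatients count as not readmitted, and that time at risk varies with LOS. If either survival or LOS differs by technique, the readmission odds ratio partly reflects time at risk.

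The effect is modest: odds ratios of roughly 1.03 to 1.16 for LOS gaps of 1 to 3 days, and risk ratios of about 1.06 to 1.16 from the plan's assumed mortality difference at equal LOS. These figures assume an equal post-discharge hazard and LOS values that the documents do not give. The direction depends on those assumptions and is not established. The missing unplanned qualifier is a separate inconsistency, subject to what Appendix 1 says. This is a worthwhile refinement of a secondary outcome, not a flaw that threatens the study.

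**What to change.** 1. Make unplanned readmission the modelled endpoint, in line with unplanned reoperation and the morbidity objective, and report any readmission descriptively. State whether readmission counts in the any-complication composite. If Appendix 1 already restricts the outcome to unplanned events, carry that wording into the Outcomes section.
2. Keep the logistic model over 30 days from surgery, and state that patients who die in hospital or remain there at day 30 count as not readmitted.
3. Add a supportive analysis in patients discharged alive before day 30, timed from discharge to postoperative day 30, with death after discharge ending follow-up. Use a time-to-event model, which compares the groups at the same time since discharge and needs no constant hazard, rather than a log-days offset.
4. Interpret both results beside mortality and LOS.

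The cost is a few lines of SAP wording and one extra analysis. The discharge day is already needed for LOS, and unplanned status is already planned for reporting. The main text does not say whether the days of readmission and death are extracted, so this should be confirmed. The extra analysis conditions on survival to discharge, which is why it is supportive only.

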We acknowledge that NSQIP is missing several important confounders, particularly in terms of having little clinical information indicating the severity of COVID infection, such as the extent of oxygen requirements or admission to higher monitoring settings. In NSQIP, “a patient who is prescribed supplemental oxygen and utilizes it on a regular basis would be assigned as dyspnea upon moderate exertion unless there is documentation of dyspnea at rest”.

Statistical Analysis

1. Preprocessing
 1. Convert age from the NSQIP character variable to continuous variable, with Age “90+” recoded as 90
 2. Standardizing the coding of missing values: missing coded in NSQIP as “-99”, “unknown”, “None Assigned”, or “NULL”. Each variable will be individually examined to ensure that the missing value is correctly standardized.
 3. Missing values
 - Patients with missing data on key variables will be excluded as described in the inclusion/exclusion criteria.
 - For confounders in modeling, if
 1. >10% missing then exclude the confounder from the model
 2. <1% missing then delete case (complete case analysis)
 3. >=1% and <10% missing then multiple imputation

- The % of missing data for height and weight will be examined in cohort characteristics. If <1% is missing, then BMI will be calculated using these variables.

4. Check for collinearity with variance inflation factor and correlation matrix: if present, combine information from collinear variables if feasible (e.g. new variables is “yes” if “yes” in any of the variables); if not, eliminate the variable that has more missing values or would be less accurately ascertained
2. Descriptive statistics
 1. Cohort characteristics (perioperative and morbidity/mortality outcomes), including by 1) COVID-positive patients by SA vs. GA, 2) COVID-negative patients January-December 2021 vs. 2017-2019, 3) COVID-positive vs. negative in January-December 2021 stratified by anesthesia technique, and 4) utilization of SA vs. GA in 2021 (January-December) vs 2017-2019. Continuous variables will be presented as mean (standard deviation) and median (IQR) for parametric and nonparametric data, respectively. Categorical variables will be presented as frequency (%). For comparison amongst groups, ANOVA will be used for parametric data, Kruskal-Wallis for nonparametric data, and Chi-square for categorical data. Standardized mean difference will be presented.
3. Multivariable logistic regression

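### No planned test or model allows for clustering by hospital, so P values and confidence intervals may be too optimistic, with the 2021 versus 2017-2019 comparisons most exposed

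*Combined protocol and SAP*

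**What the plan says.** Under Study Design the source is described as "a prospectively-collected multicentre dataset with more than 150 clinical variables within 30 days after surgery". Under Statistical Analysis, item 2 (Descriptive statistics), the groups are compared as follows: "ANOVA will be used for parametric data, Kruskal-Wallis for nonparametric data, and Chi-square for categorical data". One of the listed comparisons is "utilization of SA vs. GA in 2021 (January-December) vs 2017-2019"; another sets COVID-negative patients of 2021 against 2017-2019.

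Item 3 gives the primary analysis: "a multivariable logistic regression will be performed using a priori exposure (SA vs. GA) and confounder variables (above) for the primary outcome of mortality". For the other outcomes, "The same independent variables will be used in the multivariable logistic regressions for secondary outcomes", with a linear model on the log scale for length of stay. "Significance level will be set at P <0.05".

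Hospital is not in the list under Confounders. The regression section, the sensitivity analyses and the Limitations mention no random effect, GEE or cluster-robust variance. Two care-organisation variables are listed for description only: "Systems factors: Medical co-management, and participation in a standardized hip fracture care program". Appendix 1 (the data extraction form) is not in the text available for this review, so it cannot be judged whether the file carries a hospital identifier.

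**The concern.** All the named tests and models assume independent patients. If the choice of SA is partly a hospital habit, patients of one hospital resemble each other in exposure and, through shared care, possibly in outcome. The information in the data is then less than the patient count suggests.

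The period comparison of SA use is the most exposed. There, technique is itself the outcome, each hospital contributes many patients, and about 30,000 patients are set against 10,000. A change in a few hospitals, or a change in which hospitals report, could be declared a significant pandemic-period change. The plan foresees reduced Procedure-Targeted data collection in the pandemic (Inclusion), so a changed hospital mix is plausible. For the primary analysis, what is at stake is an interval for the SA effect that is too narrow.

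**Working it through.** **1. The plan's own figure.** Inputs from the Sample size section: mortality 36% versus 26%, SA:GA 1:4, and "With 80% power and 0.05 alpha". Two-sided pooled formula, weighted mean risk (4×0.36 + 0.26)/5 = 0.34:

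n(GA) = [1.96·√(5×0.34×0.66) + 0.8416·√(0.36×0.64 + 4×0.26×0.74)]² / 0.10² ≈ 851.3, so 852.

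Adding 213 for SA gives 1065, against 1064 stated. For 36% versus 22% the same formula gives 421 + 106 = 527, against 525. Both reproduce without a design effect, so the sample size also assumes independent patients.

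**2. Primary SA versus GA contrast.** Approximate design effect DE = 1 + (m−1)·ρx·ρy, where m is patients per hospital, ρx the ICC of technique and ρy the ICC of mortality. True type I error = 2[1 − Φ(1.96/√DE)]. N = 1000 is the plan's expectation. Hospital count (50 to 200), ρx (0.1 to 0.5) and ρy (0.01 to 0.05) are assumptions.

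| Case | DE | Type I error | Power, 36% vs 26% | N needed (1064×DE) |
|---|---|---|---|---|
| Independent | 1 | 5.0% | 77.4% | 1064 |
| Mildest: 200 hospitals, 0.1, 0.01 | 1.004 | 5.1% | 77.2% | 1068 |
| Middle: 100 hospitals, 0.3, 0.05 | 1 + 9×0.015 = 1.135 | 6.6% | 71.9% | 1208 |
| Most severe: 50 hospitals, 0.5, 0.05 | 1 + 19×0.025 = 1.475 | 10.7% | 60.0% | 1569 |

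Of the 18 combinations examined, 15 have DE below 1.15. In the most severe case the model standard error is too small by 1 − 1/√1.475 = 18%. The plan also allows for 500 patients. The middle case then has m = 5, DE = 1 + 4×0.015 = 1.06 and type I error 5.7%.

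A separate simulation with unequal hospital sizes (1000 patients, 50 to 200 hospitals, no SA effect, 4000 runs per scenario) gave rejection rates of 4.5 to 10.9%. The ratio of true to model standard error was 1.00 to 1.22, so the model value is too small by at most 1 − 1/1.22 = 18%.

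**3. SA use, 2021 versus 2017-2019.** From the plan: about 10,000 patients a year, hence 30,000 versus 10,000, and SA 20%. Assumed: 100 equal hospitals and no true average change. The chi-square variance of the difference is 0.16×(1/30,000 + 1/10,000) = 2.133×10⁻⁵. Let K = 100×(1/30,000 + 1/10,000) = 0.01333.

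- *Same hospitals, stable practice.* The variance ratio is 1 − ρ, that is 0.9 or 0.7 for ρ = 0.1 or 0.3. Type I error is 3.9% or 1.9% (simulated 3.7% and 2.2%), so the test is slightly conservative.
- *A fraction t of hospitals replaced.* The ratio is (1 − ρ) + 2tρ/K. With t = 0.2 and ρ = 0.1 it is 0.9 + 3.0 = 3.9, type I error 32% (simulated 31%). With ρ = 0.3 it is 0.7 + 9.0 = 9.7, or 53% (simulated 52%). With t = 0.1, simulation gave 21% and 38%.
- *Hospital-specific drift, mean zero, SD τ on the logit scale.* Ignoring baseline variation between hospitals, the ratio is about 1 + 0.16τ²/K. For τ = 0.2, 0.3 and 0.5 it is 1.48, 2.08 and 4.0, giving 11%, 17% and 33%. Simulations under differing hospital assumptions gave about 9 to 12%, 12 to 23% and 26 to 48%.

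**4. Mortality compared between periods.** The turnover formula does not depend on the event rate. With t = 0.2 and ρ = 0.01 to 0.05 the ratio is 0.99 + 0.30 = 1.29 to 0.95 + 1.50 = 2.45, so type I error is about 8 to 21%. The exposure is real but less than for SA use.

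**The case against.** The best case for the plan has five parts.

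- **Direction is not established.** A reader might infer that all the P values and intervals are too optimistic. The documents do not support that. With stable, identical hospitals the utilization test is slightly conservative, and in the mildest primary scenarios nothing changes. This objection stands, and the point can only be that they may be too optimistic.
- **The sizes are assumed.** Hospital count, ICC, drift and turnover appear nowhere in the documents. This stands, and the figures above are ranges under stated inputs, not estimates for this database.
- **Utilization is context.** The plan introduces it to help interpretation and lists it under Descriptive statistics. No power calculation depends on it, and standardized mean differences will be shown as well. This stands and lowers the weight. It does not make the planned chi-square P value meaningful.
- **Drift within hospitals is a real change, not chance.** This is right if the inference is confined to the hospitals in the file. It does not cover a change in which hospitals report, nor a reading of the result as a general pandemic-period shift.
- **Clustered errors may be infeasible, and they are incomplete.** No hospital identifier is listed in the available text. If hospital affects both technique and mortality, the odds ratio itself is confounded, and clustered errors leave that bias untouched. Both parts stand; the fix is therefore conditional and limited to the error bars.

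**Conclusion.** The point holds as a conditional one. The data are multicentre, every planned test and model assumes independence, and the stated sample size does too. Under the assumed ranges the primary model is usually affected little: type I error is 5 to 11%, with 6 to 7% in the middle case. It would be wrong to infer that the primary result is invalid. The period chi-square tests are the weak place: roughly 10 to 50% type I error if hospitals drift differently or the mix changes, and no inflation if neither happens. The documents do not show which applies. This is a cheap improvement to the plan, not a fault that defeats the primary objective.

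**What to change.** State in the analysis plan whether the released file carries a hospital identifier.

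- **If it does:** use hospital-clustered standard errors (sandwich or GEE) for the primary and secondary models, including log length of stay, and for the utilization and other period comparisons. Cluster on hospital across both periods, so that differing drift and turnover both enter the variance. Where multiple imputation is used, combine the clustered variances across imputations.
- **If it does not:** give the utilization and period contrasts as percentages and differences without P values. Add to the Limitations that the model intervals assume independent patients and may be too narrow.

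In either case, say that hospital may also confound the SA effect and that clustered errors do not correct for this.

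The cost is a variance option in the R analysis and somewhat wider intervals, or the loss of some descriptive P values and one added sentence.
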